This is a pilot study that aims to compare treatment for obesity in adolescents delivered via a group telehealth model with treatment provided via our traditional in-clinic Empower weight management program, in order to assess feasibility, cost-effectiveness, and efficacy of group telehealth. We will assess efficacy by measuring: (1) Changes in BMI, blood pressure, and relevant laboratory values (2) Quality of life scores (3) Self-efficacy scores (4) Patient satisfaction. Subject recruitment and study design: Patients that have been referred to Empower and the KidsNFitness program will be eligible, as well as CHLA patients seen in a multitude of environments, including outpatient clinics, the Emergency Department, the inpatient setting seen by Physical Therapy, Occupational Therapy, and Clinical Nutrition. In order to be recruited to the intervention group, participants must be between 14 and 18 years of age; informed consent will be obtained. After obtaining their consent, intervention group participants will be assigned to the intervention telehealth group (final total n=32). We plan to run two consecutive 6-month cohorts. Each cohort will consist of two telehealth groups of 6-8 participants each (total 12-16). We plan to over-enroll each group to account for expected attrition; we will enroll a minimum of 6 and maximum of 8 participants in each of the two telehealth groups, for a total of approximately 30 participants (final total n=32) between the two 6-month cohorts. Parents will be contacted on a weekly basis to update them about their child's session attendance, the general content of the sessions, and to remind them to prompt their child to log on to their twice monthly telehealth sessions. We will ask for their preferred mode of contact (text message, email, and/or phone) and use all preferred methods to contact them. Intervention group subjects will be enrolled into a group telehealth program, in which twice monthly sessions will be held using a HIPAA compliant web-based platform, for 6 months.

The intervention group will be asked to come in for in-person research visits at 0, 3 and 6 months for collection of weight, blood pressure, and other anthropometric measures; they will be asked to complete baseline, 3 month, and 6 month questionnaires regarding quality of life, self-efficacy, diet, and physical activity habits; an additional survey regarding satisfaction with treatment will be administered at end of the 6 month study period, and repeat bloodwork will be obtained at that time.

For the control group, we will use retrospective data for all eligible patients from our Empower clinic whose first clinic visit was between January 2015 and June 30, 2019. The end point for data collection will be no later than December 31, 2019. Those who are matched to the intervention group for age, gender, and severity of obesity; we will request a waiver of consent for this group.

Statistics and data analysis plans: The target recruitment of approximately 206 subjects (30 intervention and 176 control) was arrived at based on practicality and feasibility for a pilot study, and modified per recommendations of our current biostatistician, based on the limited data available upon chart review for many of the clinic control subjects. For evaluation of changes in the continuous outcomes, BMI, blood pressure, and hemoglobin A1C, triglyceride level, and ALT, assessed at baseline and immediately following the end of the 6 month intervention, we

will utilize regression analyses, which will allow us to compare the magnitude of change between the telehealth intervention and the comparison group, taking into account both change from baseline to follow-up time points as well as relevant baseline covariates. For these analyses covariates will be participants' age, gender, and presence of existing medical conditions (e.g. diabetes; rheumatologic conditions) that could affect weight loss.

Background

Prior Literature

EMPOWER is a multi-disciplinary, team-based clinic model, involving physicians, psychologists, registered dietitians (RDs), and physical therapists (PTs) providing tertiary care management of obesity. Data from the first two years of EMPOWER show that patients with four or more visits (n=109) experienced a decrease in average BMI z-score (-0.09SD). This, though modest, is promising; however, both cost and patient retention present significant challenges to EMPOWER and other tertiary care pediatric obesity programs and may be barriers to further progress. Much administrative personnel time is consumed in working with insurers in order to authorize visits, and nevertheless, this type of hospital-based care is poorly reimbursed. Getting to CHLA is often a major challenge for our patients, due to the large urban sprawl of Los Angeles, traffic, limited and expensive parking, and poor public transportation. Frequent visits result in missed work and school days, a burden to families. Our adolescent patients face even greater challenges, as they they are in the process of learning to manage their own health and balance the emotional and social changes required in the transition to adulthood, with family and parental expectations and limitations.

Rationale for this Study

Telehealth technology presents an innovative, cost-effective, and often highly engaging alternative to in-person visits, which bypasses many of the logistical difficulties of getting to CHLA. Moreover, adolescents today are highly attuned to, and aligned with, digital and mobile technologies, and are natural consumers of media in this format. There is strong evidence from numerous published studies that telehealth can be an effective tool for chronic disease management (1,2, 3). Additionally, many youth with obesity are significantly socially isolated, and our current individual patient-provider model does not effectively address this isolation in the way we expect a group session will; various published studies of group treatment have demonstrated inter-participant support and positive effects of social interaction (4, 5, 6).

While our current model leads to successful weight management in many of our patients, success is often modest, as mentioned above; and for some of our patients, it simply does not work. With this proposal, we wish to pilot a group telehealth model targeted at adolescents with obesity.

Citations:


randomized controlled trial examining peer support and behavioral weight loss treatment. Journal of Adolescence. 44:117-123.

Study Objective

Primary Aim -

To pilot a new care delivery model for adolescent patients with obesity, using group telehealth visits

Secondary Aim -

To assess the feasibility of using telehealth with adolescent patients

Tertiary Aim -

To test the efficacy of group appointments using telehealth

Rationale for the Selection of Outcome Measures

- 1. Use of shared medical appointments via telehealth is a feasible, cost-effective care delivery model for adolescents being treated for obesity.
- 2. The efficacy of this model will be comparable to, or better than, standard multidisciplinary in-person visits.
- 3. Attendance to telehealth visits will be better than attendance to standard in-person visits, as measured by no-show rates and same-day reschedules

Study Design

Overview Design Summary

There will be two cohorts for this study, each lasting 6 months. Each cohort will consist of an intervention arm of 12 subjects. We will recruit a minimum of 12 subjects, up to a maximum of 17 subjects in the first cohort and a maximum of 15 in the second cohort, this over-recruitment will attempt to account for possible attrition from the groups.

All study staff are HIPAA and CITI certified and will be trained in the use of the web-based platform. Additionally, all clinical staff conducting telehealth sessions will be oriented to the semi-structured curriculum, and the study coordinator who will also be conducting the intersession coaching will be trained and mentored by a CHLA researcher who has recently conducted a similar study utilizing a cell-phone based app and brief coaching for treatment of adolescents with obesity.

Subject Selection and Withdrawal

Inclusion Criteria

Prospective Group:

Youth age 14-18 who meet criteria for or are currently enrolled in the Empower weight management clinic will be included. These criteria include body mass index (kg/m2) that is either greater than the 99th percentile, or greater than the 95th percentile accompanied by an obesity-related comorbid condition such as hyperlipidemia, pre-diabetes or diabetes, non-alcoholic fatty liver disease (NAFLD), obstructive sleep apnea, or polycystic ovarian syndrome.

Youth will need to speak English but those whose parents' primary language is Spanish will be included.

Retrospective Control Group:

All eligible youth from our EMPOWER clinic patients whose first clinic visit occurred between January 2015 and June 30, 2019, and were 14-18 years old, were included in our control group.

Exclusion Criteria

Prospective Group: (1) significant intellectual or neurodevelopmental disability, ie previous diagnosis of autism spectrum disorder or developmental delay (2) non-English speaking; (3) age < 14 years and > 18 years (4) weight greater than 255 kg.

Given the shared nature of group appointments, participants should be at approximately the same developmental stage as their peers. Discussion topics may include stigma, body image, family dynamics, and school issues, and therefore a wide variance in age range or cognitive status could potentially diminish the effectiveness of the group sessions. Non-English-speaking youth will be excluded due to limitations in translation services for such a small pilot project. Lastly, with respect to the weight limit, we are excluding patients whose baseline weight is greater than 255 kg, because the scale we use for study visits has an upper weight limit of 272 kg. Because we anticipate that some patients will experience weight gain rather than weight loss, we are allowing for the possibility of a 17 kg weight gain over the 6-month course of the study and therefore choosing an upper weight limit which is 17 kg less than the upper limit of the scale.

Subject Recruitment Plan and Consent Process

If potential subjects are interested in hearing more about the study but unwilling to do so at their in-person Adolescent EMPOWER or other clinical encounter (i.e. outpatient clinics, Emergency Department, Physical Therapy, Occupational Therapy, and Clinical Nutrition), we will obtain their telephone or electronic contact information as well as mailing address, and permission to contact them at a later date and to mail consent forms to their electronic or physical mailing address.

If CHLA Health Network pediatricians have patients that are eligible for the study and would like to be referred, they can forward their patients' information to our study coordinator as per the attached email, and we will screen them by phone with the same recruitment screener.

Waiver of consent is being requested only for retrospective control group subjects. This is due to impracticality of obtaining consents from patients we are no longer following clinically, whereas for the telehealth intervention group, which is a prospective group, we will be obtaining informed consent from all adult participants, given the very interactive nature of the intervention. Written consent will be obtained from all subjects who turn 18 during the course of study participation. Their re-consent will be obtained via the addendum document once they turn 18 on their next visit.

Risks and Benefits

 Some of the questions may make the participant feel uneasy or embarrassed.

• There is a small risk that people who are not connected with this study will learn a participant's identity or their personal information.

- Venipuncture risks include mild discomfort (or pain), bruising and swelling around the puncture site, dizziness or fainting, or infection (rare).
- Improvement in some or all of participants' symptoms
- The advancement of knowledge
- A new treatment or therapy for the condition under study

Early Withdrawal of Subjects

 They will not be punished or denied something which they would normally receive (e.g., threatening to withdraw health services to which an individual would otherwise be entitled) if they choose not to participate in this research or choose to withdraw early from participation.

Study Procedures

Screening for Eligibility

Script to be used by study staff and email to be sent to CHLA Health Network pediatrician offices.

Schedule of Measurements

The intervention telehealth group participants will have their anthropometric measurements and vital signs recorded onto their Case Report Forms (CRFs) during their in-person baseline, 3-month, and 6-month visits. Baseline lab reports that have been obtained by primary care providers included in Empower referral packets, if applicable, will also be recorded onto the CRF, as will follow-up lab work obtained at the 6 month inperson visit. If no baseline labs have been collected in the last 6 months by referring PMD, we will collect baseline bloodwork here at the CHLA CTU.

Intervention Visits

- (1) Group telehealth sessions twice per month for 6 months. The group sessions will be 60 minutes and involve delivery of a semi-structured curriculum including topics such as nutrition education, reducing barriers to physical activity, and how to celebrate with family and friends in a healthful manner, and will use interactive activities such as photovoice (see attached curriculum). Sessions will be facilitated by EMPOWER providers (physicians, psychologists, RDs, and PTs) who will use a combination of: (1) motivational interviewing techniques, modified for the group setting, (2) supportive exploration of barriers to behavior change and (3) setting SMART goals. Beginning with cohort 2, sessions will be recorded for internal use.
- (2) Brief individualized coaching by the research team between sessions, via telephone or email. It will be comparable to the personalized feedback and motivation provided in standard EMPOWER.

(3) Parents will be contacted on a weekly basis to update them about their child's session attendance, the general content of the sessions, and to remind them to prompt their child to log on to their twice monthly telehealth sessions. We will ask for their preferred mode of contact (text message, email, and/or phone) and use all preferred methods to contact them.

- 4) All Telehealth sessions will be recorded. The recordings may include audio and video (only if the participants have their camera turned on during the session), and video of the research staff running the session. Participants will be reminded verbally before every session that they will be recorded.
 - Data collected on Experimental procedures for the telehealth group include:
 - 1. Data collection from Empower referral packets and/or the electronic medical record regarding their weight/body mass index (BMI), blood pressure, medications, and lab results, onto the CRFs. Date of study visit, and current zip code will be included, as well as preferred contact method for coaching (ie text, mobile phone, or electronic mail). If contact info itself (ie the actual mobile number or electronic mail address) must be updated, it will be documented onto the subject code list and contact info log. Unstructured notes about the telehealth sessions will be documented onto the CRFs by the session facilitator(s) and may include individual participants' level of engagement and involvement during the session, as well as noted significant changes in patient's home circumstances, life events, travel, or major illnesses.
 - 2.Twice monthly weights will be entered into the scale's app will be recorded as well.
 - 3. Missed telehealth sessions will be tallied at the final study visit for each telehealth group participant.
 - 4. Questionnaires assessing quality of life, self-efficacy, diet, and physical activity habits will be administered and collected at baseline, 3-month, and 6-month visits; at the 6-month end point they will also complete a survey about satisfaction with care. It is anticipated that it will take participants 30 to 60 minutes to complete these questionnaires, in addition to a brief visit with research staff to obtain their measurements.
 - 5.A1C, fasting glucose, fasting lipids, AST and ALT will be drawn at 6-month visit, and results will be documented as well. They will also be drawn at baseline, if participants did not have them performed as part of their clinical care during the previous 6 months. Baseline lab results will also be documented.

6.General session information for bi-weekly (every 2 weeks) telehealth sessions will be collected onto the Telehealth Session Report forms by the session facilitators, including which participants attended and how the facilitator felt the session went.

 Experimental procedures for Control Group subjects will be limited to data abstraction from the CHLA KIDS electronic medical record (EMR

Statistical Plan

As noted previously, the target recruitment of 32 intervention and 176 control was arrived at based on practicality and feasibility for a pilot study. For evaluation of changes in the continuous outcomes, BMI, blood pressure, and hemoglobin A1C, triglyceride level, and ALT, assessed at baseline and immediately following the end of the 6 month intervention, we will utilize regression methods, which will allow us to compare the magnitude of change between the telehealth intervention and the comparison group, taking into account both change from baseline to follow-up time points as well as relevant baseline covariates. For these analyses covariates will be participants' age, gender, and presence of existing medical conditions (e.g. diabetes; rheumatologic conditions) that could affect weight loss.

Update June 2021: Matched control group subjects will be identified by calculating a propensity score, by collecting data for all potential control patients seen in EMPOWER clinic in the approved date ranges. There is no change to the nature of the data points, and their data will be extracted from KIDS and entered into REDCap database as already outlined.

Update Dec 2022: Given the limited data available for each of the matched clinic control patients (many had missing lab and other values), it was determined that we should remove the "matched" inclusion criteria and collect data on all 176 eligible control patients, in order to have a statistically meaningful cohort.

Data Handling and Record Keeping

Physical data will be stored in a locked office, locked storage unit, restricted access to authorized study personnel. Electronic data will be accessed through a secure computer/laptop, individual ID plus password protection, network restrictions, security software, and access terminated when authorized personnel leaves the study.

Any audio/video recordings will not be anonymized or de-identified because they will only be used by the study staff. The recordings will be deleted at the end of the study.

Study Monitoring, Auditing, and Inspecting

Direct identifiers and/or the key to the codes will be destroyed upon completion of the research (all data/specimens will be stripped of identifying information and/or the key to codes destroyed, paper documents shredded, electronic files purged, electronic media securely erased).

Study Administration

Funding source

All costs of the research will be paid for by the sponsor/funder. The study does not include standard of care procedures; however, costs of parent or participant time off from work, transportation, parking, babysitter fees, food purchased while at the hospital, etc. will not be paid for by the study.

For participants who have not had Hemoglobin A1C, fasting glucose, AST, ALT, and fasting

lipid panel within 6 months of the start of participation, cost of phlebotomy and lab processing will be covered by CTSI voucher awarded in support of this study.

Subject Stipends or Payments

Subjects from the telehealth intervention arm will be compensated with gift cards in the amount of \$10 for completion of questionnaires at the 3-month visit and \$20 at the 6-month visit. Gift cards will be given directly to the participants, whether they are minor age teens or adults.

Publication Plan

Dissemination of findings will include sharing information in local conferences. After complete data analysis, manuscription will be submitted for publication in a pediatric weight management, or pediatric nutrition journal.

Attachments

Informed Consent Documents (separate pages)
Questionnaires or Surveys (separate pages)

References

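### Telehealth and control patients come from only partly overlapping source populations, and recruitment source appears neither in the listed data items nor in the analysis

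*Combined protocol and SAP*

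**What the plan says.** **Telehealth arm.** The opening summary, under subject recruitment and study design, first names program referrals: "Patients that have been referred to Empower and the KidsNFitness program will be eligible". It then widens the pool: "as well as CHLA patients seen in a multitude of environments, including outpatient clinics, the Emergency Department, the inpatient setting". Therapy (physical and occupational) and nutrition services are named as the inpatient contact points. The Subject Recruitment Plan and Consent Process adds a further route: "If CHLA Health Network pediatricians have patients that are eligible for the study and would like to be referred", their details can go to the study coordinator for screening. The Inclusion Criteria set the entry condition: "Youth age 14-18 who meet criteria for or are currently enrolled in the Empower weight management clinic will be included". No Empower visit or referral is required.

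**Control arm.** The Inclusion Criteria for the retrospective group take "All eligible youth from our EMPOWER clinic patients whose first clinic visit occurred between January 2015 and June 30, 2019", aged 14-18. Background describes that clinic as "providing tertiary care management of obesity".

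**Data and analysis.** The data items listed for telehealth participants under Intervention Visits include information from referral packets or the medical record "regarding their weight/body mass index (BMI), blood pressure, medications, and lab results, onto the CRFs". They also include visit date, zip code, contact preference, session notes, scale weights, missed sessions, questionnaires and bloodwork. Recruitment source is not named. The regression covariates, given in the opening summary and the Statistical Plan, are age, gender and existing medical conditions. The June 2021 update introduced a propensity score without naming its variables. The December 2022 update removed matching and took all 176 eligible controls.

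**The concern.** Each control had reached a specialty weight clinic at least once. A telehealth participant approached in the emergency department or on a ward may never have sought weight-management care. The same BMI and comorbidity criteria can make the arms alike in clinical severity without making them alike in care-seeking, motivation or access. Background itself treats access as a serious obstacle to Empower care.

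Two stated hypotheses are exposed (Rationale for the Selection of Outcome Measures): that efficacy is comparable to or better than in-person care, and that attendance is better. Attendance is the more obviously vulnerable, because it plausibly depends on the same traits that brought controls to the clinic. Run as planned, the regression attributes any remaining source difference to the mode of delivery. Without recruitment source, a reader cannot tell how many telehealth participants resemble the control population.

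**Working it through.** **1. The plan's own figure.** The opening summary gives 30 + 176 = 206, which reproduces its stated total. The Statistical Plan gives 32 + 176 = 208. Both targets rest on feasibility. No alpha, power, effect size or SD is stated, so there is no sample-size formula to check.

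**2. Sources side by side.**

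| Route | Telehealth | Control |
|---|---|---|
| Referred to Empower, or enrolled there | Admitted | All had a first Empower visit |
| Referred to KidsNFitness | Admitted | Only if they also had an Empower visit |
| Other outpatient clinics, emergency department, inpatient, therapy, nutrition | Admitted | Only if they also had an Empower visit |
| Network pediatrician referring to the study | Admitted | Only if they also had an Empower visit |

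The first row is shared ground. The other rows can bring in telehealth participants with no counterpart among the controls.

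**3. Precision of the planned contrast.** In SD units, with complete data and no covariate adjustment:

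SE = sqrt(1/32 + 1/176) = sqrt(0.03125 + 0.00568) = 0.192 SD.

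With 30 telehealth patients it is 0.198 SD.

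**4. Possible bias.** Let *p* be the share of telehealth participants from outside Empower. Let *d* be the difference in their expected 6-month change, under the same care, that the covariates do not capture. If the remaining participants resemble the controls, bias = *p* × *d*. The documents give neither quantity; the values below are assumed.

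- Low: 0.25 × 0.2 = 0.05 SD, and 0.05/0.192 = 0.26 SE
- Middle: 0.50 × 0.4 = 0.20 SD, and 0.20/0.192 = 1.04 SE
- High: 0.75 × 0.4 = 0.30 SD, and 0.30/0.192 = 1.56 SE

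With no true effect and an assumed two-sided 5% test, the false-positive rates would be 0.058, 0.18 and 0.345 respectively. The sign of *d* could go either way. This arithmetic applies to the continuous outcomes, not to attendance, for which the plan gives no scale or variance.

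**5. Precision of a restricted comparison.** The same shares leave 32 × 0.75 = 24 down to 32 × 0.25 = 8 telehealth patients from Empower:

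- 24 v 176: sqrt(1/24 + 1/176) = 0.22 SD
- 8 v 176: sqrt(1/8 + 1/176) = 0.36 SD

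**The case against.** The strongest reply is that the arms share more than a list of recruitment sites suggests. Empower referrals are the first source named, enrolled Empower patients qualify, and the Adolescent EMPOWER encounter is itself a recruitment setting. A reader might infer that the two populations are disjoint; the documents do not support that.

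Nor do they support the inference that every control had been formally referred and had obtained insurer authorisation. Background says "Much administrative personnel time is consumed in working with insurers in order to authorize visits", but does not say that each control needed or obtained it. The control definition requires only a first clinic visit. Referral from primary care does not separate the arms cleanly either: Empower referral packets carry laboratory results from primary care, and the pediatricians who may send patients to the study belong to the hospital's own network.

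The access contrast is also narrower than it looks, because telehealth participants are asked to attend in person at 0, 3 and 6 months. The covariate for existing medical conditions may absorb some difference in health. The screener and case report forms are not in the documents and may already hold the source. Finally, this is a pilot with efficacy as its tertiary aim, and broad recruitment is a reasonable choice for feasibility.

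These replies narrow the point but do not remove it. Overlap is not equivalence, and the plan neither measures the overlap nor uses it. Pilot status does not help much, since the stated aim is to compare the two models and a between-group regression is specified.

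**Conclusion.** The point holds in a limited form. The source populations overlap in part, differences in care-seeking and access can enter the BMI and attendance comparisons, and nothing in the listed data items or planned analysis shows by how much. Whether source is captured on forms that are not shown cannot be determined.

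The size and direction of any bias are unknown. The range of 0.05-0.30 SD, or 0.26-1.56 standard errors, is an illustration resting wholly on an assumed share of 25-75% and an assumed difference of 0.2-0.4 SD. The standard error of 0.192 SD assumes complete data. The protocol expects attrition and reports missing control values, so the real standard error would be larger and the ratio of bias to standard error smaller. A reader should not infer that the telehealth result is biased by any particular amount, or that it favours one arm.

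This should be corrected, because the remedy is cheap, but it does not undermine the pilot's feasibility aims.

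**What to change.** - Record, or recover from screening records, referral packets or the medical record, each telehealth participant's recruitment source: Empower referral, KidsNFitness referral, other clinic, emergency department, inpatient, therapy or nutrition service, or network pediatrician. Record separately whether the participant was referred to or enrolled in Empower. Show both in the baseline table.
- Prespecify a sensitivity analysis that repeats the BMI and attendance comparisons with the telehealth arm restricted to Empower-referred or enrolled participants. Restriction is needed because all controls share one source, so source cannot serve as an ordinary covariate.
- Report the full and restricted estimates together, each with its confidence interval. Set no rule that switches the conclusion if they disagree: with as few as 8 telehealth patients they can differ by chance, and such a rule could rest the conclusion on the smallest subset.
- Word the telehealth-versus-clinic conclusion to acknowledge the differing source populations.

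The cost is one data field, a few baseline-table rows and one additional analysis. The restricted estimate will be imprecise, with a standard error of about 0.22-0.36 SD for 24 down to 8 telehealth patients. Restriction also leaves other differences in place: consenting volunteers are still compared with routine patients, being referred is not the same as having attended, and the controls still come from an earlier calendar period fixed by the protocol.

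### Controls come from a closed 2015–2019 window and telehealth is an undated prospective group, so drift between periods goes unadjusted into the efficacy comparison

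*Combined protocol and SAP*

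**What the plan says.** The study summary draws controls from clinic patients "whose first clinic visit was between January 2015 and June 30, 2019. The end point for data collection will be no later than December 31," of that year. The Inclusion Criteria for the retrospective group repeat the window: "All eligible youth from our EMPOWER clinic patients whose first clinic visit occurred between January 2015 and June 30, 2019".

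The Subject Recruitment Plan and Consent Process justifies the consent waiver for controls by the "impracticality of obtaining consents from patients we are no longer following clinically" and sets them apart from the other arm: "whereas for the telehealth intervention group, which is a prospective group". Telehealth runs as two six-month cohorts, one after the other. No calendar date is given for either.

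The Statistical Plan compares change from baseline to 6 months by regression, and states that "covariates will be participants' age, gender, and presence of existing medical conditions (e.g. diabetes; rheumatologic conditions) that could affect weight loss". Its June 2021 update introduces a propensity score without naming the variables. Its December 2022 update drops matching and takes all 176 eligible controls. Neither update mentions visit year or period, and no sensitivity analysis is described.

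**The concern.** When one arm is drawn from a fixed past window and the other is enrolled prospectively, arm and calendar period are largely the same variable. Whatever moved the 6-month change between periods then appears in the arm coefficient. Candidates are clinic practice, referral mix not captured by the three covariates, and the background weight trajectory of adolescents. A control first seen in early 2015 counts the same as one first seen in mid-2019. Using more controls narrows the interval but leaves this bias where it is.

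What is at stake is the protocol's expectation, in its rationale for the outcome measures, that telehealth will do at least as well as in-person care. The clinic's own reported effect is modest (an average BMI z-score change of −0.09 SD in patients with four or more visits), so a modest drift could colour that conclusion. The feasibility of delivering telehealth is not affected.

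**Working it through.** There is no power-based figure to reproduce: the plan gives no alpha, power, effect size or SD, and says that the numbers were set on practicality. The two stated totals are 30 + 176 = 206 (summary) and 32 + 176 = 208 (Statistical Plan). I use 32 and 176.

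**Inputs from the documents.** Control first visits from January 2015 to 30 June 2019 (54 months); 176 controls; 32 telehealth participants.

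**Assumptions, none of them in the documents.** SD of 6-month BMI change 2 kg/m2 (range 1.5–2.5); drift in 6-month change of 0 to 0.2 kg/m2 per year; telehealth start between January 2019 and January 2021; even accrual of controls; two-sided alpha 0.05.

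**1. Gap between the arms.** The midpoint of the control window is 31 March 2017. The gap to telehealth start is 1.75 years (January 2019) to 3.76 years (January 2021).

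**2. Bias against all controls.** Bias = drift × gap. At zero drift it is 0. At 0.2 kg/m2 per year it is 0.2 × 1.75 = 0.35 to 0.2 × 3.76 = 0.75 kg/m2. The range is 0 to 0.75. This dates everyone at the first cohort's start; a second cohort six months later adds at most about 0.2 × 0.25 = 0.05.

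**3. Sampling error for comparison.** √(1/32 + 1/176) = 0.1922. The 95% half-width is 1.96 × 2 × 0.1922 = 0.75 kg/m2 (0.56 at SD 1.5; 0.94 at SD 2.5).

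**4. False-positive rate with no true effect.** For a shift of d SDs the rejection probability is Φ(d/0.1922 − 1.96) + Φ(−d/0.1922 − 1.96):

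| Shift between periods | At SD 2 | Significant result |
|---|---|---|
| 0 | 0 | 5.0% |
| 0.1 SD | 0.2 kg/m2 | 8.2% |
| 0.2 SD | 0.4 kg/m2 | 18.0% |
| 0.3 SD | 0.6 kg/m2 | 34.5% |

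**5. Restricting to recent controls.** First visits from July 2017 to June 2019 cover 24 of 54 months, so about 176 × 24/54 = 78 controls, with a mean date of about 1 July 2018. The gap falls by about 1.25 years, to 0.50–2.51 years, and the bias range becomes 0 to 0.2 × 2.51 = 0.50 kg/m2. The cost in precision is √(1/32 + 1/78) / √(1/32 + 1/176) = 0.2098/0.1922 = 1.09, about 9%. If only half the controls have usable outcomes (88, of whom about 39 are recent), the ratio is 0.2384/0.2064 = 1.155, about 15.5%.

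**6. What a slope among controls can show.** The SD of a uniform date over 4.5 years is 4.5/√12 = 1.30 years. The slope SE is 2/(√176 × 1.30) = 0.116 kg/m2 per year, so its 95% interval is the estimate ± 0.23. Power is about 14% to detect a drift of 0.1 and 41% to detect 0.2.

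**7. Adding linear calendar time to the model.** The SE of the arm effect rises from 0.192 SD to 0.240 SD for a mid-2019 start and 0.279 SD for a mid-2020 start. Without overlap in time this only extrapolates the 2015–2019 trend.

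**The case against.** A reader might infer that telehealth ran wholly after the control window, so that every change between periods is counted as a telehealth effect. The documents do not support that. A prospective arm is not necessarily a later one, no enrolment dates are given, and current clinic patients may join telehealth. The earliest start assumed above, January 2019, lies inside the control window. Overlap would shrink the bias, though what remained would still be unadjusted.

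A reader might also list changed laboratory methods as a source of bias. A constant assay shift between periods affects a patient's baseline and follow-up alike and cancels in the change. Only a shift within a patient's own six months, or drift in the change itself, would matter. Referral mix is likewise partly covered by the three covariates, so only the residual part counts.

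Nothing in the documents says that drift occurred, which is why its range here includes zero. Even the largest bias shown only equals the half-width of the interval.

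The remedies have limits too. A null slope would not exclude drift of the size considered. Agreement between the restricted and full estimates proves little, because they share the same 32 telehealth participants and about 78 controls: at SD 2 their difference has a sampling SD of 2 × √(1/78 − 1/176) = 0.17 kg/m2, against an expected difference of 0.2 × 1.25 = 0.25 at the top drift. Neither analysis removes a step change after 2019. All of this stands. It limits what may be claimed from the analyses, but does not remove the case for running them.

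Finally, efficacy is the tertiary aim of a pilot, with no margin or decision rule, and the controls are openly called retrospective. That lowers the weight of the point.

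**Conclusion.** The point holds in limited form. All controls belong to a closed window, telehealth is prospective and undated, and the planned regression does nothing about calendar time. Drift in 6-month change therefore biases the efficacy comparison by an unknown amount: 0 to 0.75 kg/m2 of BMI under the stated drift and start-date assumptions, with the top of that range equal to the 95% half-width at SD 2. The documents show neither that drift took place nor that the periods are fully separate. This should be corrected, because the result will be read as a comparison of two care models, but it does not undermine the pilot's feasibility aims.

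**What to change.** Amend the Statistical Plan as follows.

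1. State the calendar dates of both telehealth cohorts.
2. Prespecify a sensitivity analysis with the same model, limited to controls with first visits from July 2017 to June 2019, and report its estimate and interval beside the all-control result.
3. Report the slope of 6-month change on first-visit date among controls with its 95% interval, as a description and not as a test.
4. Present the efficacy result as an exploratory comparison with historical clinic patients. Do not conclude from it alone that telehealth matches or exceeds in-person care. State that neither analysis can remove a step change after 2019 if the cohorts ran after the control window closed.

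No new data are needed: the first-visit date is already required to apply the control window, and telehealth visit dates are recorded under Study Procedures. The cost is a small amount of analysis, the wider restricted interval shown above and a more cautious conclusion.
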